# 8.2.4.2. Hepatic Safety Monitoring

Participants with NASH may have normal or elevated ALT and fluctuations of ALT are part of the natural course of the disease. Therefore, assessment of possible drug-induced liver injury (DILI) must take into account the baseline ALT (Regev et al. 2019). Possible DILI will be adjudicated by a committee of physicians external to Lilly with hepatic expertise. This committee will be blinded to study assignment. Additional clinical and laboratory monitoring (Appendix 3 Section 10.3) is required if a participant experiences any of the following elevations of liver tests while in the study.

# For participants with baseline ALT <1.5 X ULN and normal baseline bilirubin:

- Elevation of ALT ≥5 X ULN
- Elevation of ALT ≥3 X ULN and presence of severe fatigue, nausea, vomiting, right upper quadrant pain
- Elevation of ALP >2 X ULN
- Elevation of TBL ≥2 X ULN

### For participants with baseline ALT $\geq$ 1.5 X ULN and normal baseline bilirubin:

- Elevation of ALT  $\ge$ 3 X baseline or  $\ge$ 300 U/L (whichever occurs first)
- Elevation of ALT ≥2 X baseline or ≥300 U/L (whichever occurs first) and presence of severe fatigue, nausea, vomiting, right upper quadrant pain
- Elevation of ALP >2 X ULN
- Elevation of TBL >2 X ULN

Baseline ALT is derived from an average of 2 pretreatment ALT measurements at least 2 weeks apart. Elevated baseline is defined as ALT  $\geq$ 1.5 X ULN. In participants with a sizable stable decrease in ALT (>50% of the baseline value) during treatment, a new baseline, corresponding to the ALT nadir, should be established on an individual basis for subsequent determination of a possible DILI signal.

For participants with Gilbert's syndrome, the criterion of elevation of TBL  $\ge 2X$  ULN should be replaced by a doubling of direct bilirubin or increased INR to > 1.5.

If a study participant meets any of the above criteria during the study, liver testing (Section 10.3) should be repeated within 48 to 72 hours including ALT, AST, ALP, TBL, direct bilirubin, gamma-glutamyl transferase, and creatine kinase to confirm the abnormality and to determine if it is increasing or decreasing. If the abnormality persists or worsens, clinical and laboratory monitoring should be initiated by the investigator and in consultation with the study medical

monitor. Monitoring of ALT, AST, TBL, and ALP should continue until levels normalize or return to approximate baseline levels.

Additional safety data should be collected via eCRF if 1 or more of the following conditions occur:

- participant meets any of the above criteria that trigger additional hepatic safety monitoring on 2 or more consecutive blood tests
- participant discontinued from treatment due to a hepatic event or abnormality of liver tests
- hepatic event considered to be an SAE

#### 8.3. Adverse Events and Serious Adverse Events

Investigators are responsible for monitoring the safety of participants who have entered this study and for alerting Lilly or its designee to any event that seems unusual, even if this event may be considered an unanticipated benefit to the participant.

The investigator is responsible for the appropriate medical care of participants during the study.

Investigators must document their review of each laboratory safety report.

The investigator remains responsible for following, through an appropriate health care option, AEs that are serious or otherwise medically important, considered related to the investigational product or the study, or that caused the participant to discontinue the investigational product before completing the study. The participant should be followed until the event resolves, stabilizes with appropriate diagnostic evaluation, or is otherwise explained. The frequency of follow-up evaluations of the AE is left to the discretion of the investigator.

Lack of drug effect is not an AE in clinical studies, because the purpose of the clinical study is to establish treatment effect.

After the ICF is signed, study site personnel will record via eCRF the occurrence and nature of each participant's preexisting conditions, including clinically significant signs and symptoms of the disease under treatment in the study. In addition, site personnel will record any change in the condition(s) and any new conditions as AEs. Investigators should record their assessment of the potential relatedness of each AE to protocol procedure or investigational product via eCRF.

The investigator will interpret and document whether or not an AE has a reasonable possibility of being related to study treatment, study device, or a study procedure, taking into account the disease, concomitant treatment or pathologies.

A "reasonable possibility" means that there is a cause and effect relationship between the investigational product, study device, and/or study procedure and the AE.

The investigator answers yes/no when making this assessment.

Planned surgeries and nonsurgical interventions should not be reported as AEs unless the underlying medical condition has worsened during the course of the study.

If a participant's investigational product is discontinued as a result of an AE, study site personnel must report this to Lilly or its designee via eCRF, clarifying if possible, the circumstances leading to any dosage modifications, or discontinuations of treatment.

#### **Serious Adverse Events**

An SAE is any AE from this study that results in one of the following outcomes:

- death
- initial or prolonged inpatient hospitalization
- a life-threatening experience (that is, immediate risk of dying)
- persistent or significant disability/incapacity
- congenital anomaly/birth defect
- important medical events that may not be immediately life-threatening or result in
  death or hospitalization but may jeopardize the participant or may require
  intervention to prevent one of the other outcomes listed in the definition above.
  Examples of such medical events include allergic bronchospasm requiring
  intensive treatment in an emergency room or at home, blood dyscrasias or
  convulsions that do not result in inpatient hospitalization, or the development of
  drug dependency or drug abuse.

All AEs occurring after signing the ICF are recorded in the eCRF and assessed for serious criteria. The SAE reporting to the sponsor begins after the participant has signed the ICF and has received investigational product. However, if an SAE occurs after signing the ICF, but prior to receiving investigational product, the SAE should be reported to the sponsor as per SAE reporting requirements and timelines (See Section 8.3.1) if it is considered reasonably possibly related to study procedure.

Study site personnel must alert Lilly or its designee of any SAE within 24 hours of investigator awareness of the event via a sponsor-approved method. If alerts are issued via telephone, they are to be immediately followed with official notification on study-specific SAE forms. This 24-hour notification requirement refers to the initial SAE information and all follow-up SAE information. Participants with a serious hepatic AE should have additional data collected using the eCRF.

Pregnancy (during maternal or paternal exposure to investigational product) does not meet the definition of an AE. However, to fulfill regulatory requirements any pregnancy should be reported following the SAE process to collect data on the outcome for both mother and fetus.

Investigators are not obligated to actively seek AEs or SAEs in subjects once they have discontinued and/or completed the study (the participant disposition CRF has been completed). However, if the investigator learns of any SAE, including a death, at any time after a subject has been discharged from the study, and he/she considers the event reasonably possibly related to the study treatment or study participation, the investigator must promptly notify Lilly.

### **Suspected Unexpected Serious Adverse Reactions**

Suspected unexpected serious adverse reactions (SUSARs) are serious events that are not listed in the IB and that the investigator identifies as related to investigational product or procedure. United States 21 CFR 312.32 and European Union Clinical Trial Directive 2001/20/EC and the associated detailed guidances or national regulatory requirements in participating countries

require the reporting of SUSARs. Lilly has procedures that will be followed for the identification, recording, and expedited reporting of SUSARs that are consistent with global regulations and the associated detailed guidances.

### 8.3.1. Time Period and Frequency for Collecting AE and SAE Information

All SAEs and AEs will be collected from the signing of the ICF through the follow-up visit at the time points specified in the SoA (Section 1.3).

Medical occurrences that begin before the start of study intervention but after obtaining informed consent will be recorded on the Medical History/Current Medical Conditions section of the CRF not the AE section.

All SAEs will be recorded and reported to the sponsor or designee immediately and under no circumstance should this exceed 24 hours. The investigator will submit any updated SAE data to the sponsor within 24 hours of it being available.

Investigators are not obligated to actively seek AE or SAE after conclusion of the study participation. However, if the investigator learns of any SAE, including a death, at any time after a participant has been discharged from the study, and he/she considers the event to be reasonably related to the study intervention or study participation, the investigator must promptly notify the sponsor.

Care will be taken not to introduce bias when detecting AEs and/or SAEs. Open-ended and non-leading verbal questioning of the participant is the preferred method to inquire about AE occurrences.

# 8.3.2. Follow-Up of AEs and SAEs

After the initial AE/SAE report, the investigator is required to proactively follow each participant at subsequent visits/contacts. All SAEs, and nonserious AEs of special interest (as defined in Section 8.3.7), will be followed until resolution, stabilization, the event is otherwise explained, or the participant is lost to follow-up (as defined in Section 1.3).

### 8.3.3. Regulatory Reporting Requirements for SAEs

- Prompt notification by the investigator to the sponsor of an SAE is essential so that legal obligations and ethical responsibilities towards the safety of participants and the safety of a study intervention under clinical investigation are met.
- The sponsor has a legal responsibility to notify both the local regulatory authority and other regulatory agencies about the safety of a study intervention under clinical investigation. The sponsor will comply with country-specific regulatory requirements relating to safety reporting to the regulatory authority, Institutional Review Boards (IRB)/Independent Ethics Committees (IEC), and investigators.
- Investigator safety reports must be prepared for SUSARs according to local regulatory requirements and sponsor policy and forwarded to investigators as necessary.
- An investigator who receives an investigator safety report describing an SAE or other specific safety information (e.g., summary or listing of SAEs) from the sponsor will

review and then file it along with the IB and will notify the IRB/IEC, if appropriate, according to local requirements.

# 8.3.4. Pregnancy

- Details of all pregnancies in female participants and, if indicated, female partners of male participants will be collected after the start of study intervention and until 1 month after the last dose of study drug for female participants and 3 months after the last dose of study drug for male participants.
- If a pregnancy is reported, the investigator should inform the sponsor within 24 hours of learning of the pregnancy and should follow the procedures outlined in Appendix 8 (Section 10.8).
- Abnormal pregnancy outcomes (e.g., spontaneous abortion, fetal death, stillbirth, congenital anomalies, ectopic pregnancy) are considered SAEs.

# 8.3.5. Medical Device Incidents (Including Malfunctions)

Medical devices (prefilled syringes) are being provided for use in this study for administration of the study drug. In order to fulfill regulatory reporting obligations worldwide, the investigator is responsible for the detection and documentation of events meeting the definitions of incident or malfunction that occur during the study with such devices.

The definition and directions for reporting of a Medical Device Incident can be found in Appendix 7 Section 10.7).

NOTE: Incidents fulfilling the definition of an AE/SAE will also follow the processes outlined in Section 8.3.2.

- The investigator will promptly report all incidents occurring with any medical device provided for use in the study in order for the sponsor to fulfill the legal responsibility to notify appropriate regulatory authorities and other entities about certain safety information relating to medical devices being used in clinical studies.
- The investigator, or responsible person according to local requirements (e.g., the head of the medical institution), will comply with the applicable local regulatory requirements relating to the reporting of incidents to the IRB/IEC.

# 8.3.6. Complaint Handling

Lilly collects product complaints on investigational products and drug delivery systems used in clinical studies in order to ensure the safety of study participants, monitor quality, and to facilitate process and product improvements.

Participants will be instructed to contact the investigator as soon as possible if he or she has a complaint or problem with the investigational product or drug delivery system so that the situation can be assessed.

# **8.3.7.** Adverse Events of Special Interest

The following are adverse events of special interest (AESI) and will be adjudicated by an external adjudication committee:

- NASH-related clinical events
- Pancreatitis
- Major adverse cardiovascular events
- Deaths

The following are additional AESI for this program that will not be adjudicated by an external committee:

- Hepatobiliary disorders
- Hypoglycemia
- Thyroid malignancies and C-cell hyperplasia
- Supraventricular arrhythmias and cardiac conductive disorders
- Diabetic retinopathy complications
- Allergic/hypersensitivity reactions. Includes injection site reactions and ADA formation.
- Severe GI AEs
- Acute renal events

Sites should collect additional details and data regarding AESIs, as instructed on the applicable eCRFs, and detailed below.

#### 8.3.7.1. NASH-Related Clinical Events

All TEAEs of cirrhosis, ascites (clinically evident), esophageal variceal hemorrhage, hepatic encephalopathy, subacute liver failure (including liver transplantation), hepatocellular carcinoma, increase in Model for End Stage Liver Disease (MELD) score >15 or liver-related mortality should be evaluated and additional diagnostic tests performed, as needed. These events will be adjudicated by an external adjudication committee.

Study drug should be discontinued for any patient who develops a clinical diagnosis of cirrhosis (e.g., evidence of hepatic decompensation, etc.) after randomization. For purposes of safety evaluation, patients with treatment-emergent cirrhosis may be followed in the study until study end, unless the investigator decides that the participant should be discontinued from the study.

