# 7. Discontinuation of Study Intervention and Participant Discontinuation/Withdrawal

# 7.1. Discontinuation of Study Intervention

Possible reasons leading to permanent discontinuation of investigational product:

- Subject Decision
  - o the participant or the participant's designee (for example, parents or legal guardian) requests to discontinue investigational product.
- Investigator Decision
  - o the investigator decides that the patient should be discontinued from the study medication
- Any medication for weight loss is given for more than 1 week
- Participants will be discontinued from the investigational product in the following circumstances:
  - o Diagnosis of cirrhosis after randomization (refer to Section 8.3.7.1 for details)
  - o Pancreatitis or pancreatic cancer (refer to Section 8.3.7.2 for details)
  - o Diagnosis of MTC after randomization
  - Diagnosis of an active or untreated malignancy (other than basal or squamous cell skin cancer, in situ carcinomas of the cervix, or in situ prostate cancer) after randomization
  - Any severe injection site reaction, or 2 or more moderate injection site reactions occurring a week or more apart
  - o Any significant study drug-related hypersensitivity reaction
  - Any TEAE, SAE, or clinically significant laboratory value for which the investigator believes that permanent study drug discontinuation is the appropriate measure to be taken
  - Any TEAE or SAE considered possibly or probably related to study drug that is severe or medically significant but not immediately life-threatening; or where hospitalization or prolongation of hospitalization is indicated; or is disabling; or limits self-care activities of daily living
  - Any TEAE or SAE regardless of attribution to study drug that has lifethreatening consequences or urgent intervention is indicated
  - o A female participant becomes pregnant
  - o Diagnosis of T1DM or latent autoimmune diabetes in adults
- If the patient develops any exclusion criteria during the course of the study, the investigator should call the sponsor to determine whether discontinuation of study drug is necessary

• Significant non-compliance with the protocol

If study drug is permanently discontinued, the patient should remain in the study if possible. The patient may continue participation in the study, attend all visits, and undergo most protocol procedures.

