# 8.1. Efficacy Assessments

# 8.1.1. Primary Efficacy Assessment

The primary efficacy measurement in this study is NASH resolution with no worsening of fibrosis based on liver histology at Week 52 compared with baseline.

In alignment with United States (US) Food and Drug Administration (FDA) draft guidance (FDA 2018) and the EMA reflection paper (EMA 2018), NASH resolution will be defined as:

- absence of fatty liver disease or simple steatosis without steatohepatitis;
- the absence of hepatocellular ballooning (NAS 0 for ballooning)
- with or without mild lobular inflammation (NAS 0 or 1 for inflammation), and
- any value for steatosis.

No worsening of fibrosis will be defined as no increase in fibrosis stage from baseline to Week 52.

Liver histology will be evaluated via liver biopsies collected at baseline in participants for whom a liver biopsy of adequate quality performed within 6 months of screening is unavailable, and at Week 52 (end-of-treatment) in all participants who remained on study drug. Patients who discontinued study drug prior to Week 36 will not have a second liver biopsy.

Histology will be scored according to the NASH CRN guidelines (Kleiner et al. 2005; Puri and Sanyal 2012). Pathologists reviewing the liver biopsies will be blinded to treatment group. Intra- and inter-observer variability in assessment of histology will be assessed. The glass slides may be scanned to facilitate future additional exploratory analyses of the whole slide images.

Liver biopsy tissue block and slides will be retained at a facility selected by Lilly or its designee for a maximum of 15 years after the last participant visit for the study, or for a shorter period if local regulations and ERBs impose shorter time limits. This retention period enables use of new technologies, response to regulatory questions, and investigation of variable response that may not be observed until later in the development of tirzepatide or after tirzepatide becomes commercially available.

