1.3. Tertiary/Exploratory Objectives

The tertiary exploratory objectives are to investigate the effect of tirzepatide 5 mg, 10 mg, or 15 mg SC QW versus placebo for:

- Additional histological measures with respect to mean change in the liver histology score from baseline for:
 - Expanded ballooning score
 - Expanded portal inflammation score
 - Expanded fibrosis Stage 1 scores
 - Mallory-Denk body score
 - Glycogenosis score

- Liver inflammation and fibrosis with respect to mean change from baseline in extracellular hepatic water content measured by iron-corrected T1 imaging (cT1, in ms) by MRI.
- Liver stiffness with respect to mean change from baseline in liver stiffness (in kPa) measured by TE.
- Liver enzymes and serum biomarkers of NASH and fibrosis with respect to mean changes from baseline in ALT, AST, GGT, K-18, Pro-C3, ELF, FIB-4, Adiponectin, Leptin, and Ferritin.
- Insulin sensitivity with respect to mean changes from baseline in fasting insulin and HOMA-IR.
- Decreasing waist circumference with respect to mean change from baseline in waist circumference (centimeters).
- PROs with respect to changes from baseline in:
 - PROMIS Fatigue short form 8a v1.0 score
 - PROMIS Pain Interference short form 4a v1.0 score
 - CLDQ-NAFLD total and domain scores
 - PGIS
- NASH resolution from baseline based on overall assessment of histology by pathologists.
- Decreasing NAS with respect to mean change from baseline in NAS on liver histology.
- Decreasing steatosis, hepatocellular ballooning, or lobular inflammation with respect to mean change from baseline in the liver histology score for:
 - Steatosis
 - Hepatocellular ballooning
 - Lobular inflammation
- Decreasing steatosis, hepatocellular ballooning, or lobular inflammation by ≥ 1 point with respect to proportion of participants that achieve a ≥ 1 -point improvement in the liver histology score from baseline for:
 - Steatosis
 - Hepatocellular ballooning
 - Lobular inflammation
- Decreasing fibrosis stage with respect to mean change from baseline in fibrosis stage on liver histology.
- Regression of fibrosis with no worsening of NASH with respect to proportion of participants with ≥ 2 -point decrease from baseline in fibrosis stage, and no worsening of NASH on liver histology.

- Prevention of progression to cirrhosis with respect to proportion of participants classified with cirrhosis (F4) on liver histology.

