- Population: participants who meet the inclusion criteria. Further details can be found in Section 5 of Protocol GPHR.
- Endpoint: NASH resolution without worsening of fibrosis at 52 weeks.
- Treatment condition: the randomized treatment.
- The ICE “permanent discontinuation of study drug” is handled by the hypothetical strategy and the potential outcome of interest is the response in the efficacy measurement if participants had adhered to the randomized treatment. There are no other defined ICES.
- Population-level summary: proportion of patients meet NASH resolution without worsening of fibrosis at Week 52.

Treatment effect of interest is thus defined as the difference in proportion of NASH resolution without worsening of fibrosis at Week 52 between QW LY3298176 (tirzepatide) and placebo. Rationale for “efficacy estimand”: This Phase 2 study aims to study the efficacy of LY3298176 (tirzepatide) under the ideal condition that all participants adhere to the randomized treatment. Data collected after the ICE will be set to missing.

Estimand(s) for Secondary Objectives

The same estimand for the primary objective will be used for the secondary efficacy endpoints for the secondary objectives.

Treatment-regimen estimand

The second estimand, the “treatment-regimen” estimand, represents the efficacy irrespective of adherence to investigational product and availability of the postbaseline biopsy. There are no ICE.

Unless specified otherwise, safety analyses will be conducted using the SS.

The end of study participation for a patient will be the earliest of date of death, date of withdrawal from further participation in the study, or date of the safety follow-up visit (Visit 801). For patients considered to be lost to follow-up, end of study participation will be the date of lost to follow-up reported by the investigator. Patient data included in the database after the last date of study participation (date of death, date of early termination or date of safety follow-up) will be excluded from statistical analyses. A listing of such data may be provided.

Summary statistics for categorical measures (including categorized continuous measures) will include sample size, frequency, and percentages. Summary statistics for continuous measures will include sample size, mean, SD, median, minimum, and maximum. The summary statistics

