3.4. Handling of Dropouts or Missing Data

For the analyses of primary and key secondary efficacy endpoints related to histology, data for participants with missing postbaseline liver biopsy will be excluded and not be imputed. A separate analysis for these endpoints may be conducted using FAS, where missing postbaseline biopsies will be imputed based on the method described in Section 3.11.1.3.

Unless specified otherwise, imputation of missing data for exploratory purposes will be limited to primary and key secondary efficacy endpoint analyses.

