3.11.2.2. Analyses of Binary Outcomes

Analyses for proportion of participants with ≥ 1 -point decrease in fibrosis stage with no worsening of NASH on liver histology Week 52 from baseline will be conducted using the same statistical models as those used for evaluating the primary objective in Section 3.11.1.1. No worsening of NASH is defined as no increase in the NAS score.

Analyses for proportion of participants with ≥ 1 -point increase in fibrosis stage as well as proportion of participants that achieve a ≥ 2 -point decrease in NAS on liver histology, with ≥ 1 -point reduction in at least 2 NAS components (steatosis, hepatocellular ballooning, lobular inflammation) at Week 52 from baseline will be conducted using the same statistical models as those used for evaluating the primary objective in Section 3.11.1.1.

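### Clinically diagnosed cirrhosis that stops study drug before Week 36 drops out of the primary, fibrosis-regression, fibrosis-progression and F4 analyses, although it is itself a progression

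*Protocol*

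**What the plan says.** Protocol 5.1 (criterion 7) admits fibrosis stage 2 or 3, and 5.2 (criterion 16) excludes stage 4. Protocol 7.1 lists a diagnosis of cirrhosis among the reasons for stopping study drug and refers to 8.3.7.1, which reads: "Study drug should be discontinued for any patient who develops a clinical diagnosis of cirrhosis (e.g., evidence of hepatic decompensation, etc.) after randomization". Staying in the study afterwards is optional and serves safety: "For purposes of safety evaluation, patients with treatment-emergent cirrhosis may be followed in the study until study end".

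On the biopsy, Protocol 8.1.1 says: "Patients who discontinued study drug prior to Week 36 will not have a second liver biopsy". For later stops, Protocol 8.1.1.3 and the early-termination footnote to the Schedule of Activities allow one within 2 weeks of the stop or last dose.

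SAP 3.2 names permanent discontinuation of study drug, for whatever reason, as the only intercurrent event. It handles this with a hypothetical strategy and adds: "Data collected after the ICE will be set to missing". SAP 3.4 says of the primary and key secondary histology endpoints: "data for participants with missing postbaseline liver biopsy will be excluded and not be imputed". SAP 3.11 applies the efficacy analysis set (EAS) without imputation to primary, secondary and exploratory endpoints alike.

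Fibrosis progression (SAP 3.11.2.2) uses the primary model. The F4 endpoint is purely histological: "Prevention of progression to cirrhosis with respect to proportion of participants classified with cirrhosis (F4) on liver histology". Neither document says how a clinical diagnosis of cirrhosis enters any of these endpoints.

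**The concern.** In most discontinuations without a biopsy, the Week 52 outcome is unknown. Here the reason for stopping is the outcome. The diagnosis comes before the drug stop and causes it, so it is on-treatment information, and SAP 3.2 describes the efficacy estimand as efficacy before discontinuation. The rule on data after the intercurrent event does not remove the diagnosis. It is lost because the endpoints accept only a biopsy reading, and the stop means that no biopsy is taken. Asking what would have happened under continued adherence does not fit a state already reached on drug.

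Fibrosis progression and F4 are therefore understated in any arm where such a case occurs. The same participant leaves the denominators of the primary and fibrosis-regression endpoints instead of counting as a failure. If the cases fall mainly on placebo, the drug's benefit is understated. If they fall mainly on active drug, the efficacy tables understate harm.

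**Working it through.** **Design figures.** Inputs (Protocol 9.2, SAP 2.2): 196 randomized 1:1:1:1, 20% dropout, 42.5% versus 12.5%, two-sided 0.05. Then 196/4 = 49 and 49 × 0.8 = 39.2 per arm, which the plan rounds to about 40. At 40 per arm, power is 86.6% by normal approximation and 82.1% by Fisher's exact test (80.8% at 39). The plan's claim of at least 80% is reproduced. The calculations below use 40 evaluable per arm.

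**Following one participant through the rules**

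| Cirrhosis first established | End biopsy | Primary, regression, progression, F4 |
|---|---|---|
| Clinically, drug stopped before Week 36 | None (Protocol 8.1.1) | Left out (SAP 3.4, 3.11) |
| Clinically, drug stopped at Week 36 or later | Optional, within 2 weeks (Protocol 1.3, 8.1.1.3) | Unclear (see below) |
| On the Week 49 to 53 biopsy, on drug | Yes | Counted |

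The second row is unclear for these reasons:
- Protocol 9.3 admits to its EAS (at least 46 weeks on drug) and its exploratory set (at least 36 weeks) a biopsy within 2 weeks of the last dose, yet excludes data after discontinuation from both.
- SAP 3.1 and 3.2 exclude data after discontinuation without an exception for such a biopsy.
- The full analysis set would keep it.

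**The optional treatment-regimen analysis.** SAP 3.11.1.2 and 3.11.2.3 say it may be run. Under SAP 3.11.1.3 a missing fibrosis score is imputed from retrieved dropouts in the same arm or, failing that, by jump to reference. Nothing fixes the score at stage 4 when cirrhosis is known, so stage 2 or 3 could be imputed. SAP 3.11 offers this analysis for primary and key secondary endpoints, not for the exploratory F4 endpoint.

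**Shift in a rate.** Let q be the observed rate among 40 and k the omitted cases. Counting them gives (40q + k)/(40 + k), a shift of k(1 − q)/(40 + k). The documents give neither q nor k; both are assumed.

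| Observed | k = 1 | k = 2 | k = 3 |
|---|---|---|---|
| 0/40 = 0% | 2.4% | 4.8% | 7.0% |
| 4/40 = 10% | 12.2% | 14.3% | 16.3% |
| 8/40 = 20% | 22.0% | 23.8% | 25.6% |
| 12/40 = 30% | 31.7% | 33.3% | 34.9% |

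One case moves the rate by 0.7/41 = 1.7 to 1/41 = 2.4 points. Three move it by 2.1/43 = 4.9 to 3/43 = 7.0 points.

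**Progression odds ratio** (illustrative, active 4/40, placebo 8/40): (4/36)/(8/32) = 0.44.
- One, two or three cases on placebo only, (4/36)/((8 + k)/32): 0.40, 0.36, 0.32.
- The same on active only, ((4 + k)/36)/(8/32): 0.56, 0.67, 0.78.

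**Primary endpoint** (planned rates, 17/40 versus 5/40; omitted cases added as non-responders; power by normal approximation)

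| Cases added | Active | Placebo | Difference (points) | Odds ratio | Power |
|---|---|---|---|---|---|
| None | 42.5% | 12.5% | 30.0 | 5.17 | 86.6% |
| 3 on placebo | 42.5% | 5/43 = 11.6% | 30.9 | 5.62 | 90.1% |
| 3 on active | 17/43 = 39.5% | 12.5% | 27.0 | 4.58 | 81.1% |
| 3 in each arm | 39.5% | 11.6% | 27.9 | 4.97 | 85.6% |

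**The case against.** The strongest reply is that these cases are neither hidden nor likely to be numerous. Protocol 8.3.7 and 8.3.7.1 send cirrhosis and related liver events to an external adjudication committee. SAP 3.14.3.2.1 reports them as counts and percentages by arm with a patient listing, and SAP 3.14 runs on the safety set whether or not an end biopsy exists. A reader might infer that the progressions are never counted anywhere; the documents do not support that. The safety count does not, however, correct the progression or F4 rates or their odds ratios.

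A reader might also infer that all cirrhosis arising on study is lost. It is not. The rule in Protocol 8.3.7.1 concerns a clinical diagnosis, and silent progression first seen on the scheduled end biopsy is counted. Entry also excludes stage 4, low platelets, low albumin, raised INR and previous decompensation, so clinical cirrhosis within 52 weeks should be uncommon. Nor can one say that every case from Week 36 is excluded, because the passages conflict.

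A clinical diagnosis is not a histological stage, and the documents do not say that each stopped case will have been confirmed before analysis. That stands, and it limits any rule to confirmed cirrhosis. It also rules out treating every transplantation, decompensation or liver-related death as F4. Protocol 8.3.7.1 lists subacute liver failure and hepatocellular carcinoma too, and a death or transplantation from these does not establish stage 4.

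Finally, this can be seen as one instance of the general complete-case approach in a study that SAP 3.6 calls exploratory. That is fair, but here the outcome is observed, so no assumption about missing data is needed to use it.

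**Conclusion.** The gap is real but narrow. A participant whose clinical cirrhosis stops drug before Week 36 leaves four efficacy analyses, although the diagnosis already settles the answer to each. The exclusion is informative, and the optional imputation does not repair it. For stops from Week 36 the finding is only that the passages are inconsistent.

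The size rests on assumed counts, since the documents give no rate of clinical cirrhosis or of progression. Each omitted case is worth about 2 points on an arm's progression or F4 rate, which can matter for endpoints with few events. The primary is little affected: even three cases in a single arm leave the risk difference between 27.0 and 30.9 points against a planned 30.0. A bias in favour of the drug might be inferred, but the direction depends on which arm has the cases and nothing in the documents predicts that. The clinical stopping rule is not at issue.

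**What to change.** Add one rule to SAP 3.2, 3.4, 3.11.2.2 and Table GPHR.3.2. Treatment-emergent cirrhosis that the external committee has adjudicated and confirmed, arising before the end-of-treatment biopsy, counts as follows whether or not a biopsy exists:
- fibrosis progression: Yes
- F4: Yes
- NASH resolution without worsening of fibrosis: No
- fibrosis regression without worsening of NASH: No

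Report this beside the biopsy-only result, naming one as main and the other as sensitivity analysis, and give the number of such cases per arm. Transplantation, decompensation or liver-related death should count as progression or F4 only where the committee also confirms cirrhosis. For the primary and fibrosis-regression endpoints these events may be scored as non-response. Carry the same rule into the imputation in SAP 3.11.1.3, so that a known stage is not overwritten.

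Separately, reconcile Protocol 1.3, 8.1.1.3 and 9.3 with SAP 3.1 and 3.2 on whether a biopsy within 2 weeks of the last dose is usable after a stop at or after Week 36.

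The rule for confirmed cirrhosis needs only SAP wording and adjudication data already planned. The downside is small: a few outcomes are classified clinically and not histologically, and the biopsy-only result shows their effect.
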